8.3.2 Direct access to source data and documents

The investigator /institution will allow site trial-related monitoring, audits, IRB/IEC review and regulatory inspections. Direct access must be provided to the CRF and all source documents/data, including progress notes, copies of laboratory and medical test results, which must be available at all times for review by the Clinical Research Associate, auditor and regulatory inspector (e.g. FDA). They may review all CRFs and informed consents. The accuracy of the data will be verified by direct comparison with the source documents described in section [8.3.1](#). The sponsor will also monitor compliance with the protocol and GCP.

8.3.3 Storage period of records

Trial site:

The trial site(s) must retain the source and essential documents (including ISF) according to the local requirements valid at the time of the end of the trial.

Sponsor:

The sponsor must retain the essential documents according to the sponsor's SOPs.

8.4 EXPEDITED REPORTING OF ADVERSE EVENTS

BI is responsible to fulfil their legal and regulatory reporting obligation in accordance with regulatory requirements.

8.5 STATEMENT OF CONFIDENTIALITY AND SUBJECT PRIVACY

Individual subject data obtained as a result of this trial is considered confidential and disclosure to third parties is prohibited with the exceptions noted in section [8.7](#).

Data protection and data security measures are implemented for the collection, storage and processing of patient data in accordance with the principles 6 and 12 of the WHO GCP handbook.

Personalised treatment data may be given to the subject's personal physician or to other appropriate medical personnel responsible for the subject's welfare. Data generated at the site as a result of the trial need to be available for inspection on request by the participating physicians, the sponsor's representatives, by the IRB / IEC and the regulatory authorities.

8.5.1 Collection, storage and future use of biological samples and corresponding data

Measures are in place to comply with the applicable rules for the collection, biobanking and future use of biological samples and clinical data, in particular

- Sample and data usage has to be in accordance with the separate biobanking informed consent
- The BI-internal facilities storing biological samples from clinical trial participants as well as the external banking facility are qualified for the storage of biological samples collected in clinical trials.
- An appropriate sample and data management system, incl. audit trail for clinical data and samples to identify and destroy such samples according to ICF is in place
- A fit for the purpose documentation (biomarker proposal, analysis plan and report) ensures compliant usage
- A fit for purpose approach will be used for assay/equipment validation depending on the intended use of the biomarker data

Samples and/or data may be transferred to third parties and other countries as specified in the biobanking ICF

8.6 TRIAL MILESTONES

The **start of the trial** is defined as the date of the enrolment of the first subject in the trial.

The **end of the trial** is defined as the 'date of the last visit of the last subject in whole trial' ('Last Subject Completed') or 'end date of the last open AE' or 'date of the last follow-up test' or 'date of an AE has been decided as sufficiently followed-up', whichever is latest.

Early termination of the trial is defined as the premature termination of the trial for any reason before the end of the trial as specified in this protocol.

Temporary halt of the trial is defined as any unplanned interruption of the trial by the sponsor with the intention to resume it.

Suspension of the trial is defined as an interruption of the trial based on a Health Authority request.

The ethics committee/competent authority in each participating EU member state will be notified about the trial milestones according to the laws of each member state.

A final report of the clinical trial data will be written only after all subjects have completed the trial in all countries (EU or non-EU), so that all data can be incorporated and considered in the report.

The sponsor will submit to the EU database a summary of the final trial results within one year from the end of a clinical trial as a whole, regardless of the country of the last patient (EU or non-EU).

8.7 ADMINISTRATIVE STRUCTURE OF THE TRIAL

The trial is sponsored by Boehringer Ingelheim (BI).

The trial will be conducted at the Human Pharmacology Centre (HPC) of BI Pharma GmbH & Co. KG, Biberach, Germany, under the supervision of the Principal Investigator. Relevant documentation on the participating (Principal) Investigators (e.g. their curricula vitae) will be filed in the ISF.

BI has appointed a Clinical Trial Leader (CT Leader), responsible for coordinating all required trial activities, in order to

- Manage the trial in accordance with applicable regulations and internal SOPs
- Direct the clinical trial team in the preparation, conduct, and reporting of the trial
- ensure appropriate training and information of Clinical Trial Manager (CT Manager), Clinical Research Associates, and investigators of participating trial sites

The trial medication will be provided by the Clinical Trial Supplies Unit, BI Pharma GmbH & Co. KG, Biberach, Germany (BI 730357) or will be obtained by the clinical trial site from a public pharmacy (itraconazole).

Safety laboratory tests will be performed by the local laboratory of the trial site

Analyses of BI 730357 and itraconazole concentrations in plasma will be performed under the responsibility of the Department of Drug Metabolism and Pharmacokinetics, BI Pharma GmbH & Co. KG, Biberach, Germany at suitable contract research organisations.

On-site monitoring will be performed by BI or a contract research organisation appointed by BI.

Data management and statistical evaluation will be done by BI or a contract research organization appointed by BI according to BI SOPs.

Tasks and functions assigned in order to organise, manage, and evaluate the trial are defined according to BI SOPs. A list of responsible persons and relevant local information can be found in the ISF.

10. APPENDICES

Not applicable.

Proprietary confidential information © 2019 Boehringer Ingelheim International GmbH or one or more of its affiliated companies

11. DESCRIPTION OF GLOBAL AMENDMENT(S)

11.1 GLOBAL AMENDMENT 1

Date of amendment	11 December 2018
EudraCT number	2018-003495-13
EU number	
BI Trial number	1407-0014
BI Investigational Medicinal Product(s)	BI 730357
Title of protocol	Relative bioavailability of a single oral dose of BI 730357 when administered alone or in combination with multiple oral doses of itraconazole in healthy male subjects (an open-label, one-way crossover study)
To be implemented only after approval of the IRB / IEC / Competent Authorities	
To be implemented immediately in order to eliminate hazard – IRB / IEC / Competent Authority to be notified of change with request for approval	
Can be implemented without IRB / IEC / Competent Authority approval as changes involve logistical or administrative aspects only	
Section to be changed	
1. Section 3.3.3, exclusion criteria 28 and 292. Section 5.2.3 (Table 5.2.3:2)
Description of change	
1. Haematological parameters added2. Interferon-γ release assay to tuberculosis added
Rationale for change	
1. Requested by Ethics Committee to exclude anaemia and infections2. To exclude subjects with tuberculosis infection

Proprietary confidential information © 2019 Boehringer Ingelheim International GmbH or one or more of its affiliated companies

11.2 GLOBAL AMENDMENT 2

Date of amendment	20 February 2019
EudraCT number	2018-003495-13
EU number	
BI Trial number	1407-0014
BI Investigational Medicinal Product	BI 730357
Title of protocol	Relative bioavailability of a single oral dose of BI 730357 when administered alone or in combination with multiple oral doses of itraconazole in healthy male subjects (an open-label, one-way crossover study)
To be implemented only after approval of the IRB / IEC / Competent Authorities	
To be implemented immediately in order to eliminate hazard – IRB / IEC / Competent Authority to be notified of change with request for approval	
Can be implemented without IRB / IEC / Competent Authority approval as changes involve logistical or administrative aspects only	
Section to be changed	Section 5.2.6.1.4 and 9.1

2. LIST OF ABBREVIATIONS

Term	Definition / description
ADS	Analysis Dataset
AE	Adverse Event
AESI	Adverse Event of Special Interest
ALT	Alanine Aminotransferase
ANOVA	Analysis of Variance
AST	Aspartate Aminotransferase
AUC _{0-tz}	Area under the concentration-time curve of the analyte in plasma over the time interval from 0 to the last quantifiable
AUC _{0-∞}	Area under the concentration-time curve of the analyte in plasma over the time interval from 0 extrapolated to infinity
BI	Boehringer Ingelheim
BMI	Body Mass Index
BP	Blood Pressure
BWU	Bioavailability/Bioequivalence, Within-Subject Design, uncontrolled
CI	Confidence interval
C _{max}	Maximum measured concentration of the analyte in plasma
CRF	Case Report Form
CTP	Clinical Trial Protocol
CTR	Clinical Trial Report
CV	Arithmetic Coefficient of Variation
DBLM	Database Lock Meeting
ECG	Electrocardiogram
EDC	Electronic Data Capture
EudraCT	European Union Drug Regulating Authorities Clinical Trials
FU	Follow-up
gCV	Geometric Coefficient of Variation
gMean	Geometric Mean
ICH	International Conference On Harmonisation
iPD	Important Protocol Deviation
ITZ	Itraconazole

Term	Definition / description
LLT	Lower Level Term
Max	Maximum
MedDRA	Medical Dictionary For Regulatory Activities
Min	Minimum
N	Number non-missing observations
O*C	Oracle Clinical
P10	10th percentile
P90	90th percentile
PK	Pharmacokinetic(s)
PKS	PK Parameter Analysis Set
PR	Pulse Rate
PT	Preferred Term
PV	Protocol Violation
Q1	1st quartile
Q3	3rd quartile
QD	Quaque die, once daily
R / Ref	Reference treatment
RAGe	Report Appendix Generator system
REP	Residual Effect Period
RPM	Report Planning Meeting
SAS®	Statistical Analysis System
SD	Standard Deviation
SOC	System Organ Class
SOP	Standard Operating Procedure
T	Test treatment
t_{\max}	Time from dosing to maximum measured concentration of the analyte in plasma
t_z	Time of last measurable concentration of the analyte in plasma
TS	Treated Set
TSAP	Trial Statistical Analysis Plan
ULN	Upper Limit of Normal

Term	Definition / description
WHO-DD	World Health Organization- Drug Dictionary
XPKISTAT	SAS [®] Macro for analysis of PK data

3. INTRODUCTION

As per ICH E9 ([1](#)), the purpose of this document is to provide a more technical and detailed elaboration of the principal features of the analysis described in the protocol, and to include detailed procedures for executing the statistical analysis of the primary and secondary variables and other data.

This trial statistical analysis plan (TSAP) assumes familiarity with the Clinical Trial Protocol (CTP), including Protocol Amendments. In particular, the TSAP is based on the planned analysis specification as written in CTP Section 7 “Statistical Methods and Determination of Sample Size”. Therefore, TSAP readers may consult the CTP for more background information on the study, e.g., on study objectives, study design and population, treatments, definition of measurements and variables, planning of sample size, randomisation.

Study data will be stored in a trial database within the Oracle ClinicalTM (O*C) system.

Pharmacokinetic (PK) parameters will be calculated using Phoenix WinNonlinTM software (version 6.3, Certara USA Inc., Princeton, NJ, USA).

The statistical analyses will be performed within the validated working environment CARE, including SAS[®] (current Version 9.4, by SAS Institute Inc., Cary, NC, USA), and a number of SASTM-based tools (e.g., macros for the analyses of AE data or laboratory data; Report Appendix Generator system (RAGe) for compilation/formatting of the CTR appendices).

4. CHANGES IN THE PLANNED ANALYSIS OF THE STUDY

All analyses as planned in the CTP will be performed and are described in more detail in this TSAP.

5. ENDPOINTS

5.1 PRIMARY ENDPOINTS

Section 2.1.2 of the CTP:

The following pharmacokinetic parameters will be determined for BI 730357:

- AUC_{0-tz} (area under the concentration-time curve of the analyte in plasma over the time interval from 0 to the last quantifiable data point)
- C_{max} (maximum measured concentration of the analyte in plasma)

5.2 SECONDARY ENDPOINTS

5.2.1 Key secondary endpoints

This section is not applicable as no key secondary endpoints have been defined in the CTP.

5.2.2 Secondary endpoints

Section 2.1.3 of the CTP:

The following pharmacokinetic parameter will be determined for BI 730357:

- $AUC_{0-\infty}$ (area under the concentration-time curve of the analyte in plasma over the time interval from 0 extrapolated to infinity)

Safety:

Section 2.2.2.2 of the CTP:

Safety and tolerability of BI 730357 and itraconazole will be assessed based on:

- *Adverse events (including clinically relevant findings from the physical examination)*
- *Safety laboratory tests*
- *12-lead ECG*
- *Vital signs (blood pressure, pulse rate)*

These parameters will be evaluated in a descriptive way only, and are therefore considered to be ‘further parameters of interest’. A confirmatory analysis is not planned.

6. GENERAL ANALYSIS DEFINITIONS

6.1 TREATMENTS

For basic study information on investigational products, assignment of treatment sequences and selection of doses, please see CTP, Section 4.

The study was performed as an open-label, one-way crossover trial with 2 treatments (T and R). It was planned to assign 14 healthy male subjects (at least 12 completed).

For details of dosage and formulation see Table 6.1: 1 below:

Table 6.1: 1 Treatments and labels used in the analysis

Treatment	Short label
R BI 730357, tablet, 50 mg, qd (Day 1)	BI
T BI 730357, 50 mg tablet, qd (Day 1) + Itraconazole 200 mg, qd (Day -3 to Day 9)	BI + ITZ

The following separate study phases will be defined for the analyses of AEs:

- **Screening** (ranging from 0:00 h on day of informed consent until first administration time of study drug)
- **On treatment**
 - **BI treatment** (including residual effect period (REP); i.e. ranging from the time of first administration of BI 730357 until 7 days thereafter)
 - **Itraconazole (ITZ)** (ranging from the time of first administration of Itraconazole until time of BI 730357 administration in treatment period 2)
 - **BI + ITZ** (including residual effect period (REP); i.e. ranging from time of BI 730357 administration in treatment period 2 until 9 days after the last administration of Itraconazole (up to 18 days))
- **Follow up**
 - **Follow-up BI** (ranging from end of BI treatment phase until next drug administration (of itraconazole) or alternatively, 0:00h on the day after trial-termination date in case of no further treatment, labelled “**FU-BI**”)
 - **Follow-up BI+ITZ** (ranging from end of BI+ITZ phase until 0:00h on the day after trial termination date, labelled “**FU-BI+ITZ**”)

Displays of AEs will be presented separately for the following treatments during on treatment phase:

- BI 730357, 50 mg tablet, qd (labelled “**BI**“)
- Itraconazole, 200 mg oral solution, qd (labelled “**ITZ**“)
- BI 730357, 50 mg tablet, qd + Itraconazole, 200 mg oral solution, qd (labelled “**BI + ITZ**“)

Two types of AE displays will be provided in the report:

A) Section 15.3 and Appendix 16.1.13.1.8 (for ClinicalTrials.gov and EudraCT) of the CTR displays:

In these displays, the on treatment phase will be analysed (labelled with the name of the study treatment (short label)). Screening and follow-up periods will not be included in this analysis.

The following totals will be provided in addition (Section 15.3 only):

- a total over all on treatment phases involving BI (“**Total on treatment BI**“)
- a total over all on treatment phases included in this analysis (“**Total on treatment**“)

B) Section 15.4 and Appendix 16.1.13.1.8 (except for ClinicalTrials.gov and EudraCT) of the CTR displays:

- Screening
- On treatment (labelled with the name of the study treatment (short label))
- Follow-up BI (labelled “**FU BI**“)
- Follow-up BI+ITZ (labelled “**FU BI+ITZ**“)

In Section 16.1.13.1.8 AE tables, the following totals will be provided in addition:

- a total over all on treatment phases involving BI (“**Total BI**“)
- a total over all study phases (“**Total**“)

Tables of vital signs and laboratory values will present results by study period including baseline of the respective period.

For detailed information on the handling of the treatments in the O*C views refer to Technical TSAP ADS plan and Analysis Data Reviewers guide.

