1.2.3 Residual Effect Period

The Residual Effect Period (REP, i.e., the period after the last dose with measurable drug levels and/or pharmacodynamic effects still likely to be present) of BI 730357 is 7 days for the mono-therapy (Treatment R). When given together with itraconazole (Treatment T), it is expected that plasma exposure of BI 730357 could be increased (albeit within the range explored in the clinical trial 1407-0001), and the time of relevant plasma exposure could be prolonged, which in turn could result in a prolonged period in which adverse effects could potentially occur.

For the use of itraconazole in Treatment T, the REP is defined as 9 days after last administration of itraconazole on Day 9 in Period 2. Therefore, the follow-up period will start earliest on Day 18 following BI 730357 dosing in Period 2, as this is expected to cover the period in which any potential adverse effects could reasonably occur.

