3. DESCRIPTION OF DESIGN AND TRIAL POPULATION

3.1 OVERALL TRIAL DESIGN AND PLAN

The study will be performed as an open-label, two-treatment, two-period, one-way crossover trial in healthy male subjects in order to compare the test treatment (T) to the reference treatment (R). The treatments will be one oral single dose of 50 mg BI 730357 as tablet formulation (tablet strength: 50 mg) together with multiple oral doses of 200 mg itraconazole as oral solution formulation (concentration: 10 mg/mL) (T) and one oral single dose of 50 mg BI 730357 as tablet formulation (tablet strength: 50 mg) given alone (R). In both treatments, BI 730357 is administered to subjects in the fasting state. In the first treatment period (Period 1, Visit 2), all subjects are planned to undergo treatment R, and in the second treatment period (Period 2, Visit 3), all subjects are planned to undergo treatment T. For details, refer to Section [4.1](#).

There will be a washout interval of at least 10 days between the administrations of BI 730357.

An overview of all relevant trial activities is provided in the [Flow Chart](#). For visit schedule and details of trial procedures at selected visits, refer to Sections [6.1](#) and [6.2](#), respectively.

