3.3.4 Withdrawal of subjects from treatment or assessments

Subjects may discontinue trial treatment or withdraw consent to trial participation as a whole ('withdrawal of consent') with very different implications; please see sections [3.3.4.1](#) and [3.3.4.2](#) below.

If a subject is removed from or withdraws from the trial prior to the first administration of trial medication, the data of this subject will not be entered in the case report form (CRF) and will not be reported in the clinical trial report (CTR). If a subject is removed from or withdraws from the trial after the first administration of trial medication, this will be documented and the reason for discontinuation must be recorded in the CRF; in addition, the data will be included in the CRF and will be reported in the CTR. At the time of discontinuation, a complete end of trial examination will be performed, if possible, and the information will be recorded in the CRF. If the discontinuation occurs before the end of the REP (see Section [1.2.3](#)), the discontinued subject should if possible be questioned for AEs and concomitant therapies at or after the end of the REP in order to ensure collection of AEs and concomitant therapies throughout the REP, if not contrary to any consent withdrawal of the subject.

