7.3.4 Safety analyses

Safety will be analysed based on the assessments described in Section [2.2.2.2](#). All treated subjects (TS, refer to Section [7.3](#)) will be included in the safety analysis. Safety analyses will be descriptive in nature and based on BI standards. No hypothesis testing is planned.

For all analyses, the treatment actually administered (= treatment at onset) to the subject will be used (any deviations from the randomised treatment will be discussed in the minutes of the Report Planning Meeting).

Treatments will be compared in a descriptive way. Tabulations of frequencies/proportions will be used to evaluate categorical (qualitative) data, and tabulations of descriptive statistics will be used to analyse continuous (quantitative) data.

Measurements (such as ECG, vital signs, or laboratory parameters) or AEs will be assigned to treatments (see Section [4.1](#)) based on the actual treatment at the planned time of the measurement or on the recorded time of AE onset (concept of treatment emergent AEs). Therefore, measurements planned or AEs recorded prior to first intake of trial medication will be assigned to the screening period, those between first trial medication intake and end of REP (see Section [1.2.3](#)) will be assigned to the treatment period. Events occurring after the REP but prior to next intake or end of trial termination date will be assigned to 'follow-up'. In case of two or more treatments, the follow-up will be summarized according to the previous treatment. These assignments including the corresponding time intervals will be defined in detail in the TSAP. Note that AEs occurring after the last per protocol contact but entered before final database lock will be reported to Pharmacovigilance only and will not be captured in the trial database.

Additionally, further treatment intervals (analysing treatments) may be defined in the TSAP in order to provide summary statistics for time intervals, such as combined treatments, on-treatment totals, or periods without treatment effects (such as screening and follow-up intervals).

Adverse events will be coded using the Medical Dictionary for Regulatory Activities (MedDRA). Frequency, severity, and causal relationship of AEs will be tabulated by treatment, system organ class, and preferred term. SAEs, AESIs (see Section [5.2.6.1](#)), and other significant AEs (according to ICH E3) will be listed separately.

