- (ii) marked haematological and other lab abnormalities or lead to significant concomitant therapy as identified by the Clinical Trial Leader/Investigator at the Report Planning Meeting.

An overall summary of AEs (including AESIs) will be presented.

The frequency of subjects with AEs will be summarized by treatment, primary system organ class (SOC) and preferred term (PT). Separate tables will be provided for subjects with other significant AEs according to ICH E3 ([10](#)), for subjects with serious AEs, for subjects with drug-related AEs, for subjects with drug related serious adverse events and for subjects with AESIs.

The SOC and PTs will be sorted by frequency (within system organ class). The MedDRA version number will be displayed as a footnote in the respective output.

In addition, frequencies of subjects with non-serious AEs that had an incidence of > 5% for at least one treatment will be summarised by treatment, primary SOC and PT.

For disclosure of adverse events on EudraCT additional information not included in a standard AE analysis will be performed. The following three entries will be created:

- Adverse Events per arm for disclosure on EudraCT
- Non-serious Adverse Events for disclosure on EudraCT
- Serious Adverse Events for disclosure on EudraCT

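### Does the itraconazole-only adverse-event phase in SAP 6.1 need a fallback end and its own follow-up phase?

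*SAP*

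**What the plan says.** Protocol 7.3.4 assigns adverse events by treatment at onset. Events from first intake to the end of the REP count as on treatment. Later events count as follow-up and are summarised under the preceding treatment. On the details it adds: "These assignments including the corresponding time intervals will be defined in detail in the TSAP".

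SAP 6.1 then lists the phases:

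- **BI:** seven days from the Period 1 dose of BI 730357.
- **ITZ:** "ranging from the time of first administration of Itraconazole until time of BI 730357 administration in treatment period 2".
- **BI + ITZ:** from the Period 2 dose of BI 730357 to nine days after the last itraconazole dose, with 18 days given as the maximum.
- **FU-BI:** from the end of the BI phase to the first itraconazole dose, "or alternatively, 0:00h on the day after trial-termination date in case of no further treatment".
- **FU-BI+ITZ:** from the end of the BI + ITZ phase to the day after trial termination.

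For CTR Section 15.3 and the registry displays, SAP 6.1 states: "Screening and follow-up periods will not be included in this analysis".

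Protocol 1.2.3 words the itraconazole REP for the planned course: "the REP is defined as 9 days after last administration of itraconazole on Day 9 in Period 2". For early stoppers, Protocol 3.3.4 says "the discontinued subject should if possible be questioned for AEs and concomitant therapies at or after the end of the REP". On spacing, Protocol 3.1 says: "There will be a washout interval of at least 10 days between the administrations of BI 730357".

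**The concern.** The ITZ phase has one stated end, and a subject can leave treatment before reaching it. The flow chart places four itraconazole doses before the Period 2 dose of BI 730357. Protocol 3.3.4.1 lets a subject stop treatment, for example because of an adverse event, and stay in the trial. For that subject:

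- FU-BI closed at the first itraconazole dose.
- The BI + ITZ phase never starts, so neither does FU-BI+ITZ.
- No follow-up phase for itraconazole alone is listed.

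The neighbouring entries do better. FU-BI has a fallback for no further treatment, and BI and BI + ITZ both include an REP. ITZ has neither, which suggests an oversight.

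The phase boundary decides whether an event enters the Section 15.3 and registry tables, because those exclude follow-up. With 14 subjects, one person can carry a preferred term past the SAP 7.8.1 threshold for non-serious events (those "that had an incidence of > 5% for at least one treatment"). The trial is open-label, so a rule settled late would be settled with the events known.

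A second point is that, at the minimum wash-out, the BI phase seems to run past the first itraconazole dose. An event in that interval would then fit two phases.

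**Working it through.** **Inputs.** Flow chart: itraconazole at −73, −49, −25 and −1 h before the Period 2 dose of BI 730357, and the last dose at 191 h (Day 9). REPs from Protocol 1.2.3: 7 days for BI 730357 alone and 9 days for itraconazole. Minimum interval between BI 730357 doses: 10 days. Planned subjects: 14.

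**1. The plan's own figure.** The last itraconazole dose plus the REP is 191 + 9 × 24 = 407 h after the Period 2 dose of BI 730357. From Day 1 at 09:00 this is Day 18 at 08:00, which agrees with the Day 18 in Protocol 1.2.3. In elapsed time it is 407/24 = 16.96 days, within the 18-day maximum in SAP 6.1.

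**2. A subject who continues.** The ITZ phase lasts 0 − (−73) = 73 h. Nothing is undefined.

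**3. A subject who stops in the lead-in.** Take the Protocol 7.3.4 rule and count nine days from the last itraconazole dose, as the BI + ITZ entry does. With the last dose at time t, the phase ends (t + 73) + 216 h after the first itraconazole dose:

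| Doses taken | Last dose, t (h) | End of REP after first dose (h) | Days |
|---|---|---|---|
| 1 | −73 | 216 | 9 |
| 2 | −49 | 240 | 10 |
| 3 | −25 | 264 | 11 |
| 4 | −1 | 288 | 12 |

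**4. Where the two readings differ for that subject.**

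| Onset of event | SAP 6.1 read literally | Protocol 7.3.4 rule |
|---|---|---|
| First itraconazole dose to end of REP | On treatment, ITZ | On treatment, ITZ |
| End of REP to last contact | On treatment, ITZ | Follow-up after ITZ |
| After last contact | Not in trial database | Not in trial database |

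Only the middle row differs. It is bounded, because Protocol 5.2.6.2.1 stops routine AE collection at the subject's end of trial, and Protocol 7.3.4 keeps events after the last per-protocol contact out of the trial database. It may be short or empty, since Protocol 3.3.4 asks for an end-of-trial examination at discontinuation and, if possible, questioning at or after the end of the REP.

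**5. Direction.** In the middle row the literal reading keeps the event in Section 15.3 and the registry displays, while the protocol rule moves it out. Neither removes it from the data. The ITZ phase does not involve BI 730357, so neither reading alters the BI or BI + ITZ columns or the on-treatment total for BI.

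**6. The 5% threshold.** One of 14 is 1/14 = 7.1%, so any single-subject event exceeds 5% in any column of 14. This reflects the trial's size and is not peculiar to the ITZ phase.

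**7. The overlap.** In hours after the Period 1 dose, the BI phase ends at 7 × 24 = 168 and itraconazole starts at 24W − 73, where W is the interval in days between BI 730357 doses.

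- W = 10: itraconazole starts at 240 − 73 = 167 h. The overlap is 168 − 167 = 1 h and FU-BI has length −1 h.
- W = 11: itraconazole starts at 264 − 73 = 191 h. There is no overlap and FU-BI lasts 191 − 168 = 23 h.
- The overlap vanishes at 168 + 73 = 241 h.

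So it needs an interval of at least 240 h and under 241 h, on clock times the flow chart calls approximate. An event in that hour is on treatment under either label. Only its column, and whether it counts in the on-treatment total for BI, is open.

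**The case for a change.** The best case for a change is that the protocol delegates these intervals to the SAP, and the SAP leaves one incomplete. Protocol 1.2.3 does not settle it unaided, because its itraconazole REP is worded for a last dose on Day 9. A follow-up event after itraconazole alone would have no listed column in the Section 15.4 displays. Stopping during the lead-in may itself be caused by an adverse event, so the subject concerned would be of interest. The repair is a few lines in SAP 6.1, needs no new data, and would remove a choice otherwise made with open-label data in hand.

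It stands that SAP 6.1 omits the case and that a careful author could have added it. It does not follow that the choice is free. The SAP says it is based on Protocol Section 7, and that section gives the default. The BI + ITZ entry supplies a count from the last itraconazole dose that is not tied to Day 9. The analyst would add a follow-up label if such a subject occurred. SAP 6.1 also refers treatment handling to a technical dataset plan that is not among the documents. It may already cover the case, though this cannot be checked and the conclusion does not depend on it.

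**Conclusion.** No change is needed. This is a gap in detail that analysts can fill from rules already written. The main point matters only if a subject starts itraconazole, does not receive the second BI 730357 dose, and has an event starting after the end of the REP (216 to 288 h after the first itraconazole dose) but before last contact. The documents give no rate for such stopping, so no expected count can be stated. The effect would be one subject's late event placed either in the ITZ on-treatment column or in follow-up, and the literal wording errs towards reporting it as on treatment. The overlap is at most 1 nominal hour, and only for intervals below 241 h.

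The affected tables are descriptive. The pharmacokinetic endpoints, the columns for BI 730357 and the stated Day 18 are untouched by the main gap, and the overlap could shift an event only between two on-treatment columns. The conclusion assumes that analysts apply Protocol 7.3.4 where SAP 6.1 is silent, and that they count the itraconazole REP from the last dose taken, as the BI + ITZ entry does.
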